5.9 Treatment Compliance

Compliance will be computed by determining the number of SC injections relative to the number of SC injections that should have been administered. The compliance will be evaluated during the double-blind period. If a subject who experience a relapse which is treated with rescue therapy and/or a protocol-defined relapse which is adjudicated by CEC or early discontinued from study treatment, the number of planned and actual SC will be counted based on the visits before the discontinuation. Treatment compliance will be summarized in terms of compliance based on the Safety population. Administration using prefilled syringe will be flagged in the listing of administration.

Compliance will be calculated using the following formula:

$$\text{Compliance (\%)} = \frac{\text{Number of SC injections during the double-blind period}}{\text{Number of planned SC injections during the double-blind period}} \times 100$$

The following summaries and listings will be provided:

- A summary table of compliance will be presented by treatment group, and overall. The number and percentage of treatment compliance will also be presented by categorized compliance as: <80%, 80%-100%, >100%,
- A by-subject listing of study drug administration as well as overall compliance during the double blind and whole period.

5.10 Efficacy Evaluation

For the definition of the double-blind period for efficacy evaluations see section 5.2. See Appendix 7.7 how to describe models with SAS code.

5.10.1 Analysis and Data Conventions

This study is designed to assess the efficacy of SA237 over placebo on the treatment of NMO/NMO-SD. The null hypothesis for primary endpoint will be that there is no difference on the TFR between SA237 and placebo during double-blinded period. The alternative hypothesis will be that there is a difference in TFR during double-blinded period.

A two-sided stratified log-rank test at 5% level will be used to test this hypothesis.

5.10.1.1 Multi-center Studies

For the purpose of the summaries and analyses, the term ‘Center’ will be used to define each site.

All centers will be pooled by country for the purpose of analysis.

Descriptive summaries will not be presented by individual center. Subject data listing will be provided by individual center.

5.10.1.2 Adjustments for Covariates

The primary efficacy analysis will be adjusted for the following baseline covariates:

- Baseline ARR: one or more than one based on the last two years before screening
- Geographic region: Asia and EU/Other.

In addition, for each covariate, a statistical test for the presence of a treatment-by-covariate interaction will be performed, by including the interaction term in the secondary analysis model. Subgroup analyses will be performed to explore the treatment-by-covariate interactions. If any of the treatment-by-covariate are found to be statistically significant, conclusions based on the secondary analysis (no interaction) will be interpreted with caution.

In addition, a Mixed-effect model repeated measures (MMRM) for secondary endpoints will be adjusted for Baseline ARR and Geographical region (stratification factors).

5.10.1.3 Handling of Missing Data

For details on censoring rule for the primary endpoint, see section 5.10.2.

For secondary continuous endpoints, a Mixed-effects model repeated measures (MMRM) analysis incorporating all data in double blind period will be used to utilize all the data collected over time with consideration of the variance-covariance matrix of the repeated measures. This method allows a general unstructured variance-covariance matrix and will include data from subjects with incomplete data from some scheduled time points.

For FACIT fatigue questionnaire, if there are less than 7 responses recorded, then the total fatigue score will be considered missing. If there are 7 or more responses recorded, then the total fatigue score for that questionnaire will be calculated as the average of the non-missing scores multiplied by 13.

5.10.1.4 Multiple Comparisons/Multiplicity

The serial gatekeeping methodology will be employed to control the rate of false positive for the primary endpoint (TFR based on protocol-defined relapses) and key secondary endpoints (change in VAS for pain at week 24 and change in the FACIT fatigue scale at week 24). The 3 efficacy endpoints will be analyzed in hierarchical order, beginning with the TFR based on protocol-defined relapses, followed by the VAS for pain, and ending with FACIT fatigue. A fixed-sequence approach will be applied to control the overall significance level at 0.05. An initial null hypothesis will be tested for the first hierarchical primary efficacy endpoint, the TFR based on protocol-defined relapses. If this is significant, then a repeat of the aforementioned testing procedure for the second hierarchical key secondary end point, the VAS for pain will be done. This will be repeated a third time for the FACIT fatigue if the VAS for pain showed a significant difference.

5.10.1.5 Examination of Subgroups

Descriptive statistics by subgroup for the demographic data, primary efficacy and key secondary variables will be presented by the defined variables in Section 5.5.

Additionally, main safety data will be presented by Japanese/Non-Japanese subgroup.

5.10.1.6 EQ-5D Scoring Algorithm

The EQ-5D 3 level version (EQ-5D 3L) descriptive system comprises the following 5 dimensions: mobility, self-care, usual activities, pain/discomfort, and anxiety/depression. Each dimension has 3 levels: no problem, some problems, and extreme problems. The scoring algorithm (US) as described in appendix 7.3 will be used but other norms may be explored for sensitivity analysis.

The EQ-5D index score will be missing in case any answer to one of the five EQ-5D dimensions is missing.

The EQ VAS records the respondent's self-rated health on a vertical, visual analogue scale ranging from 0 to 100 where the endpoints are labelled 'Best imaginable health state' and 'Worst imaginable health state'.

5.10.1.7 SF-36 Scoring Algorithm

The SF-36 is a multi-purpose, short form health survey with 36 questions. It yields an 8 scale profile (vitality, physical functioning, bodily pain, general health, role-physical, role-emotional, social role functioning and mental health) of functional health and well-being scores as well as physical and mental health component summary measures (PCS and MCS).

The SF36 will be scored using the Quality Metric proprietary scoring system (version 4.5). Component and domain scores are transformed to a 0-100 scale based on the 2009 US Normative population. Higher scores are indicative of better health related quality of life and a score of 50 is average for the US population.

For the SF-36, missing data rules will be applied according to the proprietary scoring software provided by the license holder (Maruish et al. 2011 p57 and p60).

5.10.1.8 FACIT-Fatigue Scale Scoring Algorithm

The FACIT Fatigue scale is a 13-item questionnaire that assesses self-reported fatigue and its impact upon daily activities and function over the past 7 days. As each of the 13 items of the scale ranges from 0-4, the range of possible scores is 0-52, which 0 being the worst possible score and 52 the best. Items are scored as follows: 0 = Not at all; 1= A little bit; 2= Somewhat; 3= Quite a bit; 4= Very much. All items are reverse scored except item An5 (*I have energy*) and An7 (*I am able to do my usual activities*). See Table 5-1 for further guidance.

When there are missing data, a total score is prorated from the score of the answered items, as long as more than 50% of the items are answered (i.e. a minimum of 7 of 13 items). The prorated score is calculated as the average of the non-missing scores multiplied by 13.

Table 5-1: FACIT scoring

Item code	Reverse item	Item response	Item score
HI7	4	-	=
HI12	4	-	=
An1	4	-	=
An2	4	-	=
An3	4	-	=
An4	4	-	=
An5	0	+	=
An7	0	+	=
An8	4	-	=
An12	4	-	=
An14	4	-	=
An15	4	-	=
An16	4	-	=

Sum individual item scores:
Multiply by 13:
Divide by number of items answered: _____ =FACIT
score

5.10.1.9 EDSS Scoring

The EDSS is an ordinal clinical rating scale ranging from 0 (normal neurological exam) to 10 (death due to NMO) in 0.5 unit increments that represent higher levels of disability. The EDSS scoring will be based on the score recorded on CRF.

5.10.1.10 mRS Scoring

The mRS is a 7-point disability scale that assesses the degree of disability in subjects with neurological impairment. Possible scores range from 0 (no symptom at all) up to 6 (death). The higher scores reflect increased disability. The mRS scoring will be based on the score recorded on CRF.

5.10.1.11 ZBI Scoring

The ZBI is the measurement to assess caregiver burden. The 22 items ask for the strain caregivers perceive. Responses range from 0 (never) to 4 (nearly always) with maximum score of 88. The higher the total score, the heavier the perceived burden. The ZBI scoring will be based on the score recorded on CRF. For summary tables, only questionnaire with responses to 17 or more out of 22 questions ($\geq 75\%$ valid response) are used.

The ZBI can be scored if 17 or more items are completed. Interpretation approach can be used if at least 75% of the items have been completed:

1. Sum the items that were answered.
2. Divide the sum by the number of items that were answered to yield the mean response per item.
3. Multiply the mean response per item by 22 (the total items in the scale).

5.10.1.12 Visual acuity function (Snellen chart)

Visual acuity will be measured by a Snellen 20-foot wall chart. The test will be performed monocularly and subjects may use their habitual distance glasses or contact lenses. If visual acuity is less than 20/200, these data will be recorded on CRF as below:

- If the subject can count fingers, this is recorded as “20/300” (CF).
- If the subject can see finger movements, this is recorded as “20/400” (HM).
- If the subject can perceive the flashlight, this is recorded as “20/500” (LP).
- If the subject cannot perceive the flashlight, this is recorded as “20/600” (NLP).
-

In order to calculate change from baseline, visual acuity scores will be converted to logMAR visual acuity scoring. Transformation of scores will be conducted based on the following table. If the record of visual acuity score (Snellen chart) is worse than 20/200 (i.e. CF, HM, LP or NLP in this study), the score will be converted to logMAR 1.85, logMAR 2.00, logMAR 2.70 and logMAR 3.00, respectively. If score which is not in the table is recorded, it would adjust to the following lower one (e.g. 20/27 will be converted to 20/30).

Table 5-2: logMAR visual acuity scoring

Snellen chart	LogMAR
20/10	-0.30
20/12.5	-0.20
20/15	-0.12
20/16	-0.10
20/20	0.00
20/25	0.10
20/30	0.18
20/32	0.20
20/40	0.30
20/50	0.40
20/60	0.48
20/63	0.50
20/70	0.54
20/80	0.60
20/100	0.70
20/114	0.76
20/125	0.80
20/150	0.88
20/160	0.90
20/200	1.00
CF	1.85
HM	2.00
LP	2.70
NLP	3.00

5.10.2 Primary Efficacy Variable

The primary efficacy analyses will be based on the ITT population. Supportive evaluations will be performed using the PPS population.

The primary efficacy endpoint is TFR based on protocol-defined relapses confirmed by the CEC with EDSS/FSS assessment performed by the examining assessor within 7 days after relapse symptoms were reported to site by the subject. TFR is defined as the time from the date of the randomization until the first occurrence of relapse throughout the study. Time point of relapse onset is defined as time at which the subject experiences any new or worsening neurological NMO representing clinical relapse(s) which is later confirmed by the CEC as protocol-defined.

Censor is defined as the earliest day of 1) the end of double blind period for efficacy analysis, 2) switching or increasing the baseline treatment (for details on the identification of the switch and increase in baseline therapy see appendix 7.4), or 3) receiving rescue therapy for clinical relapse.

The primary analysis of the study is to test the equality of the TFR distribution based on protocol-defined relapse in the SA237 + baseline treatment (SA237) and Placebo + baseline treatment (placebo) arms:

$$H_0: TFR_{SA237} = TFR_{\text{placebo}} \text{ versus } H_1: TFR_{SA237} \neq TFR_{\text{placebo}}$$

A stratified two-sided log-rank test using strata of baseline ARR (one vs. more than one) and geographical region (Asia and EU/Other) will be used.

The Kaplan-Meier method will be used to estimate the TFR based on protocol-defined relapses distribution for each treatment group. The Kaplan-Meier curve will provide a visual description of the differences across treatment groups. In addition, estimates of the treatment effect will be expressed as hazard ratio and 95% CIs using a stratified (baseline ARR and geographical region) Cox proportional-hazards model (Exact method will be used for tie data). Treatment by covariate interactions will be assessed by including the pairwise interaction terms in the Cox proportional-hazards model.

The following summary tables, figures and analysis will be provided for the ITT and PPS:

- A summary table of Kaplan-Meier estimate of TFR (protocol-defined relapse) will be presented by treatment group.
- A figure of Kaplan-Meier estimate of TFR (protocol-defined relapse) will be presented by treatment group.
- Analysis of TFR (protocol-defined relapse) will be performed using the stratified log-rank test.
- Analysis of TFR (protocol-defined relapse) will be performed using the stratified Cox regression.

The subgroup forest plot of HR of TFR (protocol-defined relapse) will be presented by the defined variables in Section 5.5.

Additionally, summary tables of sensitivity analysis of TFR (clinical relapse), TFR (treated clinical relapse), TFR (treated clinical relapse: optic neuritis) , protocol-defined relapse

based on CEC adjudication (regardless of assessment limit of 7 days) and protocol-defined relapse based on EDSS/FSS increase relative to baseline will be conducted for ITT as follows. All relapses reported by investigators will be handled as events for TFR (clinical relapse). Relapses treated with rescue therapy will be handled as events in addition to protocol-defined relapses for TFR (treated clinical relapse). Relapses treated with rescue therapy and judged optic neuritis by investigator will be handled as events in addition to protocol-defined relapses for TFR (treated clinical relapse: optic neuritis). Optic neuritis will be identified via relapse assessment form before data base lock (for details see appendix 7.4).. The same censoring rules as for the primary endpoint will be applied, except for the specific event of interest.

- A summary table of Kaplan-Meier estimate of TFR (clinical relapse) will be presented by treatment arm.
- A summary table of Kaplan-Meier estimate of TFR (treated clinical relapse) will be presented by treatment arm.
- A summary table of Kaplan-Meier estimate of TFR (treated clinical relapse: optic neuritis) will be presented by treatment arm.
- A summary table of Kaplan-Meier estimate of TFR (protocol-defined relapse based on CEC adjudication (regardless of assessment limit of 7 days)) will be presented by treatment arm.
- A summary table of Kaplan-Meier estimate of TFR (protocol-defined relapse based on EDSS/FSS increase relative to baseline) will be presented by treatment arm.
- A figure of Kaplan-Meier estimate of TFR (clinical relapse) will be presented by treatment group.
- A figure of Kaplan-Meier estimate of TFR (treated clinical relapse) will be presented by treatment group.
- A figure of Kaplan-Meier estimate of TFR (treated clinical relapse: optic neuritis) will be presented by treatment group.
- Analysis of TFR (clinical relapse) will be performed using the stratified log-rank test.
- Analysis of TFR (treated clinical relapse) will be performed using the stratified log-rank test.
- Analysis of TFR (treated clinical relapse: optic neuritis) will be performed using the stratified log-rank test.
- Analysis of TFR (clinical relapse) will be performed using the stratified Cox regression.
- Analysis of TFR (treated clinical relapse) will be performed using the stratified Cox regression.
- Analysis of TFR (treated clinical relapse: optic neuritis) will be performed using the stratified Cox regression.

- Analysis of TFR (protocol-defined relapse based on CEC adjudication (regardless of assessment limit of 7 days)) will be performed using the stratified Cox regression.
- Analysis of TFR (protocol-defined relapse based on EDSS/FSS increase relative to baseline) will be performed using the stratified Cox regression.
- TFR (clinical relapse) is defined if the relapse will be reported in eCRF. TFR (treated clinical relapse) is defined if the subject received rescue therapy for clinical relapse.
- A by-subject listing of TFR, which also includes clinical relapse, treated clinical relapse, treated clinical relapse: optic neuritis, will be provided.

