Subjects who experience a relapse which is treated with rescue therapy and/or a protocol-defined relapse which is adjudicated by CEC in the double-blind period or who complete the double-blind period can enter the open-label extension period. In the extension period, subjects can receive open-label treatment with 120 mg SA237 SC at Weeks 0, 2 and 4 and Q4W thereafter, until commercial availability of SA237 or Sponsor's decision of discontinuation of the development program in combination with a baseline treatment or as a monotherapy. This is the discretion of the Investigator to modify the baseline treatment after the double-blind period of this study. For subjects who are treated with rescue therapy during the double-blind period, SA237 can be started once disease has stabilized after rescue therapy for relapse (Day 31 or later but not more than 60 days, where Day 1 is defined as the day of onset of relapse in the double-blind period). The subjects who are not treated with rescue therapy during the double-blind period can enter the extension period after 4 weeks from the last dosing in the double-blind period.

Figure 1: Study Design

Subjects who withdraw from the study in the double blind period due to clinical relapse should be asked to continue Safety Follow-Up (SFU) for a period of 24 weeks from the last dose of study drug.

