- A by-subject listing of analysis population (ITT, PPS, SAF, All SA237, PK-PPS, Adolescents Population, and PK-Adolescents Population) information will be provided.

This listing should include: subject number, inclusion/exclusion flag for each population and reason for exclusion from each population.

Subgroup analysis will be conducted based on the following variables:

- Age category (<18, ≥18 years)
- NMO/NMOSD and AQP4 Status at screening (5 categories: NMO, NMOSD, NMO and AQP4 positive, NMO and AQP4 negative, and NMO/NMOSD and AQP4 positive)
- Baseline treatment (azathioprine, mycophenolate mofetil, oral corticosteroids, azathioprine + oral corticosteroids, mycophenolate mofetil + oral corticosteroids)
- Baseline ARR (1, >1) based on the last two years before screening
- Geographic region (Asia, Europe/other)
- Japanese, Non-Japanese subjects
- ADA status (ADA negative subjects, ADA unaffected subjects, Treatment-boosted ADA subjects, Treatment-induced ADA subjects) (see Section 5.13)

For safety analyses, baseline weight (<median, ≥median) will be included in addition.

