5.6 Demographic and Other Baseline Characteristics

Summary tables and listing will be provided as follows for ITT, PK-PPS and SAF:

- Demographics will be summarized as collected at screening or baseline visit before administration of first dose of study drug and will include gender, race (American Indian/Alaska Native, Asian [Japanese], Asian [Non-Japanese], Black/African American, Native Hawaiian/other Pacific Islander, White and Other), Geographic region (Asia, Europe/other), age (years), age category (<18, ≥18), ethnicity, racial subgroup, height, body weight (the first and the third quartiles of body weight will be presented), body mass index (BMI, kg/m²), BMI category (<18.5, ≥18.5 to <25, ≥25 to <30, and ≥30 kg/m²), Baseline ARR (1, >1) , AQP4 status at screening (positive, negative), Diagnosis (NMO, NMOSD) and Baseline treatment (azathioprine, mycophenolate mofetil, oral corticosteroids, azathioprine + oral corticosteroids, mycophenolate mofetil + oral corticosteroids) by treatment group and overall.

- A by-subject listing of demographic data.

Age will be calculated as the number of complete years between a subject's birth date and the date of the first informed consent.

The subgroup summary tables will be presented for ITT and SAF by the defined variables with the exception of ADA status (See section 5.5).

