5.10.3 Secondary Efficacy Variables

The key secondary efficacy endpoints are change from baseline in VAS for pain score and the FACIT fatigue scale score at week 24. All efficacy analyses will be based on the ITT population in double-blind period.

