5.13 Immunogenicity

ADA subgroup using confirmatory sample status are defined as below.

- ADA negative subjects: subjects without positive ADA during study. If sample at baseline is missing and no sample after the the baseline is positive, the subject is defined as "ADA negative subjects".
- ADA unaffected subjects: subjects who have pre-existing ADA (POSITIVE at baseline) that was NOT boosted to a higher level after the post dose. "NOT boosted to a higher level" means that ADA titer after the baseline is <fourfold than the ADA titer at baseline.
- Treatment-boosted ADA subjects: subjects who have pre-existing ADA that was boosted to a higher level at least one time point after baseline "Boosted to a higher level" means as follow
 - 1) ADA titer after the baseline is greater fourfold than the ADA titer at baseline
- Treatment-induced ADA subjects: subjects who have positive ADA not at baseline but after the baseline. If sample at baseline is missing and at least one sample after the baseline is positive, the subject is defined as "Treatment-induced ADA subjects"

The immunogenicity will be analyzed using the SAF population.

- The numbers and proportions of subjects with positive ADA at baseline will be presented by treatment group and overall.
- The numbers and proportions of ADA negative subjects, ADA unaffected subjects, treatment-boosted ADA subjects, and treatment-induced ADA subjects will be

summarized. The numbers and proportions of transient ADA and persistent ADA will be summarized in the treatment-induced ADA subjects.

Transient ADA: 1) Treatment-induced ADA detected only at one sampling time point (excluding the last sampling time point) during the study or 2) treatment-induced ADA detected at two or more sampling time points during the study, where the period between first and last ADA-positive sampling time points is less than 16 weeks, and the subject's last sampling time point is ADA-negative.

Persistent ADA: 1) Treatment-induced ADA detected at two or more sampling time points during the study, where the period between first and last ADA-positive sampling time points is 16 weeks or longer or 2) where the period between first and last ADA-positive sampling time points is less than 16 weeks, and the subject's last sampling time point is ADA-positive or 3) treatment-induced ADA detected only at the last sampling time point.

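### The TFR forest plot in SAP 5.10.2 takes in ADA status, a post-randomisation category with no proper placebo counterpart; ADA should be left out of this exploratory plot (minor)

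*SAP*

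**What the plan says.** SAP 5.10.2 sets the subgroup display for the primary endpoint: "The subgroup forest plot of HR of TFR (protocol-defined relapse) will be presented by the defined variables in Section 5.5". SAP 5.10.1.5 adds tables from the same list: "Descriptive statistics by subgroup for the demographic data, primary efficacy and key secondary variables will be presented by the defined variables".

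The list in SAP 5.5 mixes baseline factors (age, diagnosis and AQP4 status, baseline treatment, baseline ARR, region, Japanese or not) with "ADA status (ADA negative subjects, ADA unaffected subjects, Treatment-boosted ADA subjects, Treatment-induced ADA subjects". Neither 5.10.2 nor 5.10.1.5 leaves ADA out. The one place that does is SAP 5.6, on demographics: "The subgroup summary tables will be presented for ITT and SAF by the defined variables with the exception of ADA status".

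SAP 5.13 defines the categories. For example, "ADA negative subjects: subjects without positive ADA during study". Treatment-induced means positive after baseline but not at baseline. Unaffected and boosted need a positive baseline and are separated by the later titre. SAP 5.13 limits the by-visit ADA table to the satralizumab arm. It does not say how placebo patients enter an ADA row of an efficacy plot.

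Protocol 2.5 lists clinical response by ADA status as an immunogenicity endpoint, and Protocol 6.8 calls for efficacy to be summarised by ADA status. Neither asks for a hazard ratio against placebo within ADA categories.

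**The concern.** A subgroup hazard ratio is a randomised comparison only if membership is fixed before treatment can influence it. ADA status is not. A satralizumab patient becomes treatment-induced positive only by staying relapse-free and on study long enough for antibody to appear and be sampled. A patient who relapses early tends to remain in the ADA-negative group, whether or not ADA matters. Placebo patients have no corresponding sorting, because during the double-blind period they have no drug to raise antibody against.

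Followed literally, the plot would set an essentially empty row and a row that is not a randomised comparison beside valid baseline subgroups, in the same format and with no warning. A reader could take the ADA-negative row as the effect in patients without antibody, or contrast it with other rows to judge whether ADA weakens efficacy. It supports neither use.

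**Working it through.** **1. Which samples define the categories.** SAP 5.13 does not define the study period it refers to. The double-blind reading is the better supported: SAP 5.10 says "For the definition of the double-blind period for efficacy evaluations see section 5.2" and SAP 5.10.3 says "All efficacy analyses will be based on the ITT population in double-blind period". The rest uses that reading.

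**2. Inputs from the plan (SAP 5.14).** 35 patients per arm; placebo hazard 0.4184 per year; HR 0.335, so satralizumab hazard 0.4184 × 0.335 = 0.1402; 2-year dropout 10%, so dropout hazard −ln(0.9)/2 = 0.0527; one year of accrual plus 1.5 years.

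**3. The plan's own figure.** Schoenfeld: 4(1.960 + 0.842)² / (ln 0.335)² = 31.4 / 1.196 = 26.2 events; power at 26 events is 79.6%. Expected events per arm are 35 × the mean, over follow-up x uniform from 1.5 to 2.5 years, of [λ/(λ+δ)] × [1 − exp(−(λ+δ)x)]. This gives 18.9 placebo and 8.1 satralizumab, 27.0 in all, consistent with 26.

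**4. Inputs from outside the SAP.**
- ADA-positive share: 41% of satralizumab patients (Protocol 5.1.1.6). This is a double-blind result reported in protocol Version 11, after this SAP (20 April 2018, written against protocol version 8.0). It is used only for illustration.
- Timing of ADA onset: not in the documents. Assumed uniform over 0-3, 0-6, 0-12 or 0-24 months, independent of relapse.
- No effect of ADA on relapse, and no assay positives on placebo: both assumed.

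**5. Treatment-induced row.** 0.41 × 35 ≈ 14 satralizumab patients against essentially no placebo patients. No hazard ratio can be estimated. This does not depend on onset timing.

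**6. ADA-negative row.** 35 − 14.35 ≈ 20.7 satralizumab patients against nearly all 35 placebo patients. Simulation with 2,000,000 patients per arm, scaled to 35, with the susceptible fraction (42%, 43%, 45%, 52%) set to give 41% positive. Hazard ratios are from Cox models in 200,000 per arm. ADA-negative satralizumab events = 8.1 − 14.35 × (share of ADA-positive patients who relapsed). Approximate 95% CI = HR × exp(±1.96 × √(1/d₁ + 1/18.8)), where d₁ is that event count and 18.8 the simulated placebo events.

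| Assumed onset | ADA-neg. satralizumab events | ADA-neg. HR v placebo (true 0.335) | Approx. 95% CI | Relapsed within satralizumab, ADA-pos. v ADA-neg. | Rate ratio within satralizumab |
|---|---|---|---|---|---|
| 0-3 months | 4.9 | 0.352 | 0.13-0.95 | 22% v 24% | 0.88 |
| 0-6 months | 5.1 | 0.372 | 0.14-0.99 | 21% v 25% | 0.77 |
| 0-12 months | 5.5 | 0.408 | 0.16-1.06 | 18% v 27% | 0.60 |
| 0-24 months | 6.1 | 0.472 | 0.19-1.18 | 14% v 30% | 0.37 |

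First row: √(1/4.9 + 1/18.8) ≈ 0.51, so the interval is 0.352 divided and multiplied by about 2.7.

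**7. Sensitivity.** With 35% to 47% positive, the ADA-negative HR runs from 0.35 to 0.52. A constant onset rate of 0.33 per year gives 0.463.

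**8. Within-arm table.** The last two columns show that a table confined to the satralizumab arm carries the same time bias: with no true ADA effect, ADA-positive patients still appear to relapse less.

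**The case against.** Much of the opposing case stands.

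- **SAP 5.10.1.5 is not at fault in itself.** It promises descriptive statistics, names no hazard ratio or test by ADA, and helps deliver the endpoint in Protocol 2.5 and 6.8. The between-arm format is explicit only in the 5.10.2 forest plot. Its overlap with SAP 5.6 on demographics is a matter of tidiness, since the specific exception would normally govern.
- **The numerical effect is modest.** The ADA-negative hazard ratio is off by at most 0.472/0.335 = 1.4-fold in the main scenarios. Every value still favours satralizumab, and with fast onset the shift is negligible. An empty row would print as not estimable, not as a wrong number.
- **No decision rests on these rows.** The only subgroup-linked action named is the companion diagnostic in Protocol 6.5.3.3, which turns on AQP4 status.
- **The replacement table is more distorted in relative terms:** up to 1/0.37 = 2.7-fold. A footnote discloses this but does not correct it. A landmark or time-dependent model would reduce the bias, but about 8 satralizumab events are expected, about 2 of them before Week 24.
- **Placebo assay positives are possible.** Protocol Table 6 samples ADA without regard to arm, and SAP 5.13 would label any new positive treatment-induced. No rate is given, so the row is essentially empty, not provably so.

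A reader might infer something stronger: that the ADA categories run into the extension. Placebo patients in the treatment-induced row would then be largely those covered by "Subjects who experience a relapse which is treated with rescue therapy and/or a protocol-defined relapse which is adjudicated by CEC", who went on to satralizumab, so the row would be selected on the outcome. The open wording in SAP 5.13 does not exclude this, but SAP 5.10 and 5.10.3 tie efficacy to the double-blind period. Any size would rest on assumed rates of rescue without a qualifying relapse and of entry to the extension, which the documents do not give. No figure is offered for it.

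**Conclusion.** The point holds as a minor one about an exploratory display. As written, SAP 5.10.2 calls for hazard ratios against placebo by a category formed after randomisation. The treatment-induced row would be essentially non-estimable. The ADA-negative row would not be a randomised comparison, with a hazard ratio of about 0.35 to 0.47 where the truth is 0.335. That range rests on the plan's hazards, 41% ADA-positive, no ADA effect, no placebo positives and the assumed onset windows. It is small beside the sampling error of 5 to 6 satralizumab events.

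A reader might also infer that the primary result is compromised, or that ADA weakens efficacy. The documents support neither. The primary log-rank test, its alpha, the 26 events and the fixed sequence do not use ADA status, and the shift arises in a calculation where ADA has no effect. Reporting efficacy by ADA status is a planned and legitimate aim; only the comparison with placebo is wrong.

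**What to change.** 1. **SAP 5.10.2:** repeat for the forest plot the ADA exclusion already written in SAP 5.6.
2. **SAP 5.10.1.5:** keep efficacy by ADA status only as a descriptive summary within the satralizumab arm, with no comparison against placebo. This meets Protocol 6.8. Carry over the SAP 5.6 exception for demographics.
3. **SAP 5.10.1.5 or 5.13:** state that ADA samples up to the end of the double-blind period define the categories for this summary.
4. **Footnote to that table:** patients who relapse early have less time to become ADA-positive, so lower relapse among ADA-positive patients is expected even if ADA has no effect (rate ratios of about 0.88 to 0.37 under the assumptions above). The table cannot show whether ADA affects efficacy.

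The cost is one clause, two short wording changes and a footnote. No new data are needed, since ADA is already sampled at nearly every dosing visit. If the outputs exist, the ADA rows can be dropped from the plot.
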